Considering the large and assumedly increasing number of patients undergoing surgery, the large number of studies that have shown that meniscal resection increases the risk for knee osteoarthritis, the documented favorable effects of exercise therapy, the scarce documented long-term effects of partial meniscal resection surgery, and the lack of knowledge upon natural development without surgery, there is need for more high quality long-term follow-up randomized controlled studies (RCTs) of the long term effect of exercise therapy versus partial meniscal resection for patients with degenerative meniscal tears.

In this RCT we randomized 140 middle-aged patients (35-60 years) with MRI-verified degenerative medial meniscal tears and no or early knee osteoarthritis (Kellgren-Lawrence (KL) grade of 0, 1 or  $2^{12}$ ) to treatment with either arthroscopic partial meniscal resection or a 12-weeks exercise therapy program^24. The primary outcome is change in knee function measured by KOOS4, a composite of four of the five subscales in the knee specific questionnaire KOOS (Knee injury and Osteoarthritis Outcome Score), from baseline to the 2-year follow-up (Figure 1).

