## 2.4. Descriptive Assessments

Baseline characteristics will be presented in a table (Table 2).

Furthermore, the following treatment-related variables will be presented descriptively:

- Compliance with exercise during the 12 weeks is recorded from the patients exercise diary notes. The patients were instructed to complete two to three exercise sessions a week over twelve weeks (24-36 sessions). Compliance is assessed as the total number of exercise sessions completed out of the minimum of 24 sessions. *Excellent compliance* is defined as participation in 24 or more sessions (more than 100 %), *satisfactory compliance* is defined as 19-23 sessions (80-100 %) and *poor compliance* is defined as 18 or less sessions (less than 80 %). Less than 80 % compliance is defined as not completed treatment allocation.
- 2) Pain level during the 12 weeks exercise treatment is recorded from the patients exercise diary notes where they have reported pain on a visual analogue scale (VAS) during and after each training session.
- Satisfaction with the treatment effect will be registered at each follow-up until 12 months on a five-point Likert scale (very dissatisfied, dissatisfied, neither satisfied nor dissatisfied, satisfied, very satisfied).
- 4) Patients crossing over from the exercise group to arthroscopy and patients in both groups going through additional surgeries during the 24 months follow-up period will be registered (Table 3).
- 5) Patients crossing over from the arthroscopy group to exercise, not have had postoperative active physiotherapy (exercises) more than 80 % of twice a week in 12 weeks (19 or more sessions)(equivalent to 80 % in the exercise group).
- 6) Adverse events (AE) and seriously adverse events (SAE) will be registered and categorized into index knee or sites other than index knee. The project workers will record any adverse events that the participant experiences or tells them about and at all follow-ups all participants are asked about potential adverse events. For all participants in both groups including all patients crossing over (see section 2.7.1.) to the other intervention a project worker will look through hospital records to register if any pre-defined perioperative or postoperative adverse events occurred, or adverse events related to the exercise therapy (Table 1).

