The KOOS subscales Pain, Symptoms, ADL, Sport/Rec and QOL, EQ- 5D Index, EQ-5 VAS, weight and global knee function will be presented as mean (with 95% CI) for each treatment group. Between-group differences in change from baseline to 2 years will be statistically assessed. Each subscale of the KOOS will be presented graphically for its development over the 2 years period.

All issues during the trial found in the treatment records from the project physiotherapist, hospital records or the questionnaire from the follow-ups will be assessed to determine whether it represents an AE or not. AE will be presented in a table (see Table 1) and analyzed statistically by comparing actual numbers of serious AE (site other than index knee, index knee and all serious events) and non-serious AE (site other than index knee, index knee and all serious events).

AE associated with surgery will be given in Table 1 for the following groups:

1. Those receiving arthroscopic meniscal resection by randomization

2. All treatment dependent AE reported during and after surgery in those who had surgery even though randomized to the exercise therapy throughout the follow up period

AE associated with exercise therapy will be given in Table 1 for the following groups:

1. Those remaining in the 'Exercise therapy' group throughout the follow up period

2. All treatment dependent AE reported prior to the surgery in those who had surgery even though randomized to the exercise therapy

3. Those randomized to surgery but crossing over to exercise during the follow-up period

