## 3. Study Design

#### 3.1. Sample Size

Primary outcome for the RCT is the ITT- analysis of the between-group difference in change in KOOS4 from baseline to the 2-year follow-up.

We wanted to detect a 10-points difference ( $\Delta$ ) with a standard deviation (SD) of 15, with a level of power ( $\beta$ ) of 90% and a level of significance ( $\alpha$ ) of 0.05. The calculation was performed using this formula, where the f ( $\alpha$ ,  $\beta$ ) is a constant (given by Stuart J. Pocock; "Clinical trials. A practical approach":

 $2 \times SD^2 / \Delta^2 \propto f(\alpha, \beta) = 2 \times 15^2 / 10^2 \times 10.5 = 47.25 \approx 48$  (patients in each group)

Estimated dropout rate at 2 years was 15%, thereby, the number of subjects (N) randomized was to be:

N - (15 % out of N) = 47.25 $N = 55.6 \approx 56 \text{ (patients in each group)}$ 

Thus, 112 patients randomized to two groups are necessary for the ITT-analysis.

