## 5.2. Secondary Endpoints

Secondary outcomes are between- and within-groups comparisons of the change from baseline to the 2-year follow-up in all secondary endpoints except for the isokinetic muscle strength and functional performance data, where 1-year follow-up is the end point.

All outcomes will be checked for normality and statistical methods will be dependent on data distribution. When fulfilling the requirements for regression analyses, ANOVA analyses of the ITT populations will be conducted; otherwise non-parametrical tests will be used.

Finally, PP- and AT-analyses will be conducted in a range of secondary outcomes.

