# 9. Tables

# 9.1. Table 1. Adverse events

Adverse events	Exercise therapy	Arthroscopic	p-values
	group	surgery group	
Seriously adverse even	nts (SAE)		
Site other than the inde	x knee, n (%)		
Cardiovascular			
Gastrointestinal			
Other			
Index knee, n (%)			
Pain			
Swelling			
Subjective instability			
Decreased range of			
motion			
Infection			
Deep vein			
thrombosis/pulmonary			
embolus			
Adverse events (AE)			
Site other than the index knee, n (%)			
Index knee, n (%)			

9.2.	Table 2	2. Base	line cł	naracteristics
------	---------	---------	---------	----------------

Baseline characteristics	Exercise therapy	Arthroscopic surgery
	group	group
Men, n (%)		
Right knee, n (%)		
Age (years), mean (median)		
Weight, mean (median)		
Body mass index, mean		
(median)		
Smoking, n (%)		
Previous smoker n (%)		
Analgesics daily n (%)		
Education level, n (%)		
Primary school		
University level		
Activity level, mean (range)		•
Level		
Sessions per week		
Hours per week		
Intensity		
Duration of symptoms, mean (mea	lian)	
2-12 months		
>12 months - 2 years		
> 2years		
Radiographic knee OA severity (k	Kellgren- Lawrence), n (%)	
Grade 0		
Grade 1		
Grade 2		
MRI; medial meniscus: degenerat	on grade, n (%)	
Grade 1		
Grade 2		
Grade 3		
Grade 4		
MRI; medial meniscus: localization	n of tear, n (%)	1
Posterior horn		
Corpus		
Anterior horn		
MRI; medial meniscus: tear morph	nology, n (%)	1
Non		
Horizontal		
Vertical		
Radial		
Longitudinal		
Root tear		
Complex		
Flap dislocated to medial recess		
Flap not dislocated		

MRI; medial meniscus: extrusion, n (%)			
None			
< 25 %			
25-49 %			
50-75 %			
> 75 %			
MRI; lateral meniscus: tear, n (%)			
KOOS scores, mean (median) (rar	nge)		
KOOS			
Pain			
Symptoms			
ADL			
Sport/Rec			
QOL			
Global knee rating, mean (median	) (range)		
Much better			
Better			
Unchanged			
Worse			
Much worse			
SF-36, mean (median) (range)			
Physical component summary			
(PCS)			
Mental component summary			
(MCS)			
Muscle strength and performance, mean (median) (range)			
Hamstrings			
Quadriceps			
One leg hop test			
6 meter timed hop test			
Knee bending test			

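### Adverse events are compared as event totals in 2.7.2 but shown as n (%) with p-values and no stated denominator in Table 1, and the two columns can share patients

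*SAP*

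**What the plan says.** The rule for comparing harms is in SAP section 2.7.2: AE are tabulated in Table 1 and "analyzed statistically by comparing actual numbers of serious AE", by site and in total, and the same is said of non-serious AE. The total is named as a total of events. The bracket for non-serious AE again names its total as serious events, apparently a copying slip.

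The same section then says who and what fills each column of Table 1. Some entries are groups of people. Others are sets of events. One entry in the exercise column is "All treatment dependent AE reported prior to the surgery in those who had surgery even though randomized to the exercise therapy"; events during and after surgery in those same patients go to the surgery column.

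Table 1 (section 9.1) has rows labelled n (%), one column per treatment group and a column of p-values. It does not say whether n counts patients or events, what the percentage is taken over, or which test gives the p-value.

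Section 2.4 lists AE under a sentence saying that "the following treatment-related variables will be presented descriptively". Section 5.2 gives a general rule for secondary outcomes: ANOVA if its requirements are met, "otherwise non-parametrical tests will be used".

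**The concern.** A number of events and a percentage of patients are different quantities as soon as one patient has more than one event. Repeats are possible here. Under section 2.4 staff record any AE they hear of and ask about AE at every follow-up, and section 2.7.2 adds the physiotherapist and hospital records as sources. Events in one patient tend to go together, and a test that treats event totals as independent counts then understates the variance.

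The second difficulty is the columns. A patient randomised to exercise who later has surgery can contribute events to both. A patient randomised to and receiving surgery who then completes 19 or more supervised sessions counts as a crossover to exercise (section 4.1), and so also meets an entry in each column. A two-sample test assumes separate groups, and a percentage needs a denominator that these columns do not have.

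At stake is how far the harms comparison between surgery and exercise can be trusted. Section 7 makes the SAP the statistician's work description, so the choice of unit would be left to the analyst.

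**Working it through.** The SAP states no AE rate or AE test result, so there is no figure of its own to reproduce. The check asks what happens if the rule is followed literally.

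**Inputs**
- Patients: "In this RCT we randomized 140 middle-aged patients" (section 1). Arm sizes are not stated; 70 per arm is assumed.
- Significance level: 5% two-sided, assumed for AE. The SAP gives 0.05 for the sample size in 3.1.
- Test: none is named. The simplest comparison of totals *a* and *b* is assumed, z = (a − b)/√(a + b).
- Events per patient: not given; 0.1 to 1.0 assumed.
- Clustering: not given; a ratio of per-patient variance to mean (VMR) of 1 to 5 assumed.

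**Formula.** With equal arms and no true difference, independent Poisson counts give Var(a − b) = E(a + b). With clustering, Var(a − b) = VMR × E(a + b), so z has standard deviation √VMR. The false-positive rate is 2 × [1 − Φ(1.96/√VMR)].

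| VMR | 1.96/√VMR | Formula | Simulated, 1.0 event per patient |
|---|---|---|---|
| 1 | 1.960 | 0.050 | 0.050 |
| 1.5 | 1.600 | 0.110 | 0.100 |
| 2 | 1.386 | 0.166 | 0.154 |
| 3 | 1.132 | 0.258 | 0.251 |

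The simulation drew Poisson or negative-binomial events per patient, 4,000 runs per setting for the z-test. At VMR 5 it gave 0.377.

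**Rare events.** At 0.1 events per patient the z-test gave 0.046 to 0.087 and an exact binomial test on the totals 0.023 to 0.060. The negative-binomial VMR is 1 + mean/k. With k from 2 down to 0.25 and a mean of 0.1, it reaches only 1.05 to 1.4, so the same patient heterogeneity does less harm when events are few.

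**Patient-level tests.** Over the same settings, counting patients with at least one event gave 0.020 to 0.043 with Fisher's test and 0.042 to 0.057 with chi-square. A Mann-Whitney test on events per patient gave 0.037 to 0.064. These results are for two separate arms of 70. They do not carry over to columns that share patients.

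**Direction of error in one comparison.**
- Suppose 3 of 70 patients in one arm have 15 events between them, and 15 of 70 in the other have one each. Totals of 15 and 15 give p = 1.00, while Fisher's test on 3/70 against 15/70 gives p = 0.004.
- Suppose 3 of 70 are affected in each arm, with 3 events in one and 15 in the other. The exact binomial p-value on the totals is 2 × (1 + 18 + 153 + 816)/2^18 = 1,976/262,144 = 0.008, although the numbers of affected patients are identical.

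The choice of unit alone can therefore reverse the conclusion either way.

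**The case against.** A reader might infer that the SAP treats repeat events as independent and that its AE p-values are therefore too small. The document does not support this. It names no AE test and never mentions independence. In Tables 2 and 3, n (%) counts patients (men, smokers, crossovers), and Table 1 can be read in the same way. The rank test that section 5.2 allows could be run on each patient's count, which roughly holds its level. The 15 against 15 example shows that an event count can also give a p-value that is too large.

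Three further points stand. The inflation figures rest on assumed clustering. Pain, swelling and reduced motion appear in Table 1 under serious events, so frequent repeats in those rows cannot be presumed. And section 2.4 lists AE as descriptive, so no decision hangs on the p-values.

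These points limit the claim but do not remove it. The wording in 2.7.2 speaks of numbers of AE, names an event total and allocates events to columns, so the event count is the literal reading. Section 5.2 does not settle the matter: AE are not among the secondary outcomes listed in 2.2, the rule there concerns intention-to-treat populations, and a two-sample rank test cannot be run on columns in which one patient may appear twice. The p-value column shows that a test is intended.

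**Conclusion.** The concern holds as a conditional one. Sections 2.7.2 and 9.1 do not fit together on unit or denominator, and the literal reading compares event totals. If those totals are tested as independent counts, the false-positive rate is about 11%, 17% and 26% at assumed variance-to-mean ratios of 1.5, 2 and 3, and about 5 to 9% at 0.1 events per patient. It stays at 5% if events do not cluster. That the p-values will in fact be too small cannot be concluded from the SAP.

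The overlap between columns does not depend on assumed rates. It follows from the column definitions whenever a crossover patient has events both before and after surgery, and it would spoil a patient-level test on those columns as well. Importance is minor to moderate: AE are supportive here, but a comparison of surgery with exercise needs a sound account of harms.

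**What to change.** In section 2.7.2:
- Make the patient the unit of any tested comparison: the number with at least one serious event, and separately with at least one non-serious event, by randomised arm.
- Use the number randomised to each arm as denominator, and give a risk difference, its 95% CI and an exact test.
- Show event totals, and the table by treatment received with the crossover split, descriptively and without p-values.
- Correct the non-serious bracket so that its total refers to non-serious events.

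Head Table 1 *patients with at least one event, n (%)*, and align section 2.4 with the one comparison that is tested.

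The cost is a few sentences and a table heading, with no new data. The downside is that repeat events are described but do not enter the test. Analysis by randomised arm also attributes events after a crossover to the allocated treatment, which is why the descriptive table by treatment received should stay beside it.

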## 4. Study Population

#### 4.1. Subject Disposition

Study procedures, including recruitment strategies and inclusion and exclusion criteria, have been described in the PhD protocol (Appendix 1). Patients included in the trial were randomized to: A) Exercise therapy or B) Arthroscopic partial meniscal resection. All consecutive patients who came to the two inclusion sites on the days of the orthopedic surgeons outpatient clinic fulfilling the eligibility criteria were asked to enter the study. Patients fulfilling all eligibility criteria, but refusing to participate in the randomization, were registered.

Crossovers are a common problem in studies randomizing to surgical or non-surgical treatments. In this study participants who experienced impairment of their symptoms or lack of improvement during the 2-year observation period, were reassessed at any time when necessary by the orthopedic surgeon who was responsible for the study. Indication for surgery (crossing over from exercise to arthroscopy) or re-operation (meniscal re-resection or other surgery in the index knee within 2 years) was based upon patient's history, clinical and radiological examinations.

Patients from the arthroscopy group that had postoperative active exercise therapy supervised by a physiotherapist more than 80 % of twice a week in 12 weeks (19 or more sessions)(equivalent to 80 % in the exercise group) were regarded as crossing over to the exercise group.

The frequency of crossovers from exercise to arthroscopy and vice versa, re-operations with meniscal re-resections or other surgery in the index knee within 2 years will be registered and reported (Table 3).

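### Crossover patients sit in both adverse-event columns of Table 1, surgery-to-exercise crossovers have no rule placing their events, and the p-values compare groups that share patients

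*SAP*

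**What the plan says.** Section 2.7.2 builds Table 1 from two lists of patients.

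- **Surgery list.** Group 1 is "Those receiving arthroscopic meniscal resection by randomization". Group 2 covers exercise-arm patients who were later operated on: "All treatment dependent AE reported during and after surgery in those who had surgery".
- **Exercise list.** It is introduced by "AE associated with exercise therapy will be given in Table 1 for the following groups". Group 1 is those who stayed with exercise. Group 2 is "All treatment dependent AE reported prior to the surgery in those who had surgery even though randomized to the exercise therapy". Group 3 is "Those randomized to surgery but crossing over to exercise during the follow-up period".

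Section 4.1 says who group 3 is. "Patients from the arthroscopy group that had postoperative active exercise therapy supervised by a physiotherapist" for 19 or more sessions "were regarded as crossing over to the exercise group".

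The same part of 2.7.2 says that events will be "analyzed statistically by comparing actual numbers of serious AE", and likewise for non-serious events. No test is named. The Table 1 shell (section 9.1) has one exercise column and one surgery column, entries as n (%), and a column of p-values. No denominators are given.

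**The concern.** Because the section 4.1 crossover is defined by exercise after the operation, everyone in exercise group 3 has already been operated on and is also in surgery group 1. For the opposite crossover the SAP divides events at the operation. For this one, surgery group 1 has no end point and exercise group 3 has no starting point.

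Two things follow. First, the statistician, for whom section 7 makes this SAP the working instruction, cannot tell where to enter knee pain, swelling, instability or loss of motion in an operated patient who is also exercising. Second, the two columns share patients, and an ordinary two-group test assumes that they do not. What is at stake is the safety comparison between surgery and exercise, in a trial whose SAP itself describes crossover as a common problem. The primary KOOS4 analysis is not affected.

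**Working it through.** **The plan's own figures.** The SAP states no adverse-event count, no crossover count and no size for either arm, so there is no figure to reproduce on this point. It does give 140 randomised (section 1) and 64 surgical procedures in total (section 3.2).

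**Step 1: who is in which column.** Let k be the number of arthroscopy-arm crossovers to exercise and m the number of exercise-arm crossovers to surgery.

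- By section 4.1 the k patients had surgery, so all k are in surgery group 1. They are also exercise group 3.
- The m patients are in surgery group 2 (events from surgery on) and in exercise group 2 (events before surgery).
- Persons in both columns: k + m. If every arthroscopy-arm patient was operated on, column memberships total 140 + k + m for 140 people.

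**Step 2: the rules for events, side by side.**

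| Crossover | Surgery column | Exercise column |
|---|---|---|
| Exercise to surgery (m) | treatment-dependent events during and after surgery | treatment-dependent events before surgery |
| Surgery to exercise (k) | no time limit | no time limit |

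The m patients' events are placed once, although the patients themselves appear twice. The k patients' events have only the two column headings to place them.

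**Step 3: how much could turn on it.** All inputs here are assumptions: 70 per arm, all arthroscopy-arm patients operated on, patients with an event 14/70 (surgery) and 4/70 (exercise), a 20% event rate among the k, and m = 0. The test is Fisher's exact, two-sided.

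By randomised arm: 14/70 (20.0%) v 4/70 (5.7%), p = 0.021.

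With the k patients added to the exercise denominator, there are two extremes:

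- A: their events stay in the surgery column only, so the exercise column is 4/(70 + k).
- B: their events are all ambiguous and entered in both columns, so the exercise column is (4 + 0.2k)/(70 + k).

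| k | A: exercise column | A: p | B: exercise column | B: p |
|---|---|---|---|---|
| 5 | 4/75 = 5.3% | 0.0105 | 5/75 = 6.7% | 0.0252 |
| 10 | 4/80 = 5.0% | 0.0056 | 6/80 = 7.5% | 0.0306 |
| 20 | 4/90 = 4.4% | 0.0024 | 8/90 = 8.9% | 0.0627 |
| 30 | 4/100 = 4.0% | 0.0016 | 10/100 = 10.0% | 0.0760 |

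The same clinical events give a p-value above or below the by-arm one, depending on a choice that the SAP leaves open.

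**Step 4: independence.** Under B, the k patients carry the same outcome into both columns. For a common event rate, the variance of the difference is proportional to 1/70 + 1/(70 + k) − 2k/[70(70 + k)]; a standard test omits the last term. For k = 10 this is 0.02679 without the term and 0.02321 with it, so the standard error is too large by √(0.02679/0.02321) = 1.074. For k = 5, 20 and 30 the factors are 1.036, 1.155 and 1.243. Under A, a patient's entries in the two columns are different outcomes. Their correlation is unknown, and the standard formula is still not justified.

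**The case against.** The strongest reply is that the two lists say whose records are searched, while their headings limit which events enter: those associated with surgery, and those associated with exercise. Section 2.4, item 6 draws the same line, separating perioperative and postoperative events from events related to exercise, and it includes crossovers.

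This reply defeats a stronger reading that a reader might infer, namely that every event of these patients is entered twice, so that an infection or deep vein thrombosis before the first exercise session would count against exercise. The SAP does not say that. It leaves double entry possible for ambiguous events and does not prescribe it. What the headings lack is any rule for deciding association. Section 2.7.2 describes only deciding whether an issue is an adverse event at all.

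Other points for the plan:

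- Group 3 may have been meant for patients who exercised instead of having surgery, which would remove that overlap. But section 4.1 defines the crossover by postoperative sessions.
- The comparison may be of events and not of persons. If each event were placed once, no event would be duplicated. But the shell asks for n (%), and the columns would still share patients.
- Reporting harms by treatment received is a deliberate and reasonable choice. A by-arm p-value charges surgical complications of exercise-arm crossovers to the exercise arm. That is a fair cost, and it is why the treatment-associated columns should stay.
- Adverse events are listed among the descriptive assessments in section 2.4. True, but 2.7.2 and Table 1 add a formal comparison.
- Any numerical effect rests on invented counts. This stands in full. It would also be wrong to add crossovers to the exercise numerator while keeping its denominator at 70, since that exaggerates the shift.

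**Conclusion.** The point holds in this form: by the SAP's own definition, arthroscopy-arm crossovers belong to both adverse-event groups, and they lack the time split given to exercise-arm crossovers. Exercise-arm crossovers are also in both columns as persons. The Table 1 p-values on n (%) would therefore compare overlapping groups, and a standard two-group test is not valid for them. This survives even perfect attribution of each event.

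Neither the size nor the direction of the effect can be determined, because k, m and the event counts are not given. On the assumed counts the effect is modest with few crossovers: at k = 10, p is 0.0056 to 0.0306 against 0.021 by arm. Under extreme B, p exceeds 0.05 at k = 20 and 30. These figures illustrate sensitivity and estimate nothing about this trial. The matter should be corrected before the safety table is produced; it does not touch the primary result.

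**What to change.** In section 2.7.2 and the Table 1 shell:

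1. State a rule that places each event of a surgery-to-exercise crossover in one column only. For example, it goes in the exercise column only if it began after the first supervised session and is judged related to exercise; otherwise it goes in the surgery column.
2. State the denominator of every column, and whether n counts patients or events.
3. Compute the p-values by randomised arm, with each patient appearing once, and name the test.
4. Keep the treatment-associated columns alongside, descriptively and without p-values.

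A time or attribution rule alone would settle the events but leave the shared patients in both columns, including the exercise-arm crossovers; step 3 is what removes that.

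The cost is a few lines of SAP text and a revised shell with extra columns. The by-arm p-value will count surgical events of exercise-arm crossovers in the exercise arm, so it should be read with the treatment-associated columns beside it.
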